Appendix 2-10 Constant Shoulder Score Physician Investigator Examiner Section115

Appendix 2-11 Summary of MMT Functions:118

Appendix 2-11 Constant Score Calculations120

1 Protocol Summary

Title:	A Prospective, Randomized, Multicenter Study Comparing the Safety and Effectiveness of ArthroX's Eclipse™ Shoulder Prosthesis to the Univers™ II Shoulder Prosthesis in Patients with a Degenerative Joint Disease
Purpose:	The purpose of this study is to demonstrate non-inferiority of the ArthroX Eclipse™ Shoulder Prosthesis to the ArthroX Univers™ II Shoulder Prosthesis for the treatment of degenerative joint disease in subjects who are candidates for total shoulder replacement. Non-inferiority in terms of safety and effectiveness will be measured by a 2 year composite clinical success (CCS) that requires functional improvement, radiographic success, absence of reoperations and revision, and lack of serious device-related adverse events.
Study Design:	Prospective, randomized, multi-center, clinical study, up to 20 sites will randomize up to 350 subjects who are candidates for a Total Shoulder Arthroplasty, to 2 treatment groups in a 2:1 (Eclipse: Univers II) fashion. This study will cease enrollment and be terminated if the Eclipse Shoulder Prosthesis receives 510 (k) clearance prior to all subjects completing the study.
Study Hypothesis:	The goal of the study is to determine that the Eclipse™ Shoulder Prosthesis is non-inferior to the Univers™ II Shoulder Prosthesis.
Investigational Arm:	ArthroX Eclipse™ Shoulder Prosthesis (Eclipse)
Control Arm:	ArthroX Univers™ II Shoulder Prosthesis (Universe II)

- Study Population:** The population for this study will consist of males and females 21 years of age and older who are candidates for a total shoulder joint replacement where the humeral head and neck are of sufficient bone stock and the rotator cuff is intact or re-constructible for one of the following indications: Osteoarthritis, avascular necrosis, post-traumatic arthritis, or rheumatoid arthritis. Additionally, the subject is not a candidate for a hemi-humeral arthroplasty and has continued symptoms in target shoulder despite at least six months of other treatment modalities (anti-inflammatory, physical therapy and steroid injections).
- Primary Objective:** The primary safety and effectiveness objective for this study is to demonstrate that the expected proportion of patients to achieve a Month 24 Composite Clinical Success (CCS) criterion among patients implanted with the investigational device (ArthroX's Eclipse) is clinically non-inferior to a control device (ArthroX's Univers II). The Composite Clinical Success endpoint contains the following components:
- Functional improvement as reflected in the Adjusted Constant score change from baseline to Month 24 clinical visit,
 - Radiographic outcome success at Month 24,
 - Absence of reoperations and revisions to the exact two-year anniversary of the index surgery, and
 - Lack of serious device related complications to the exact two-year anniversary of the index surgery
- Primary Endpoint:** The primary safety and effectiveness endpoint is a composite of the following:
- An improvement in the Adjusted Constant Score (for pain, function and range of motion) from baseline (pre-op) to the Month 24 time-point that is ≥ 10 points and a final Adjusted Constant Score ≥ 54 .
 - Radiographic success at the Month 24 time-point, which is defined as absence of clinically significant humeral radiolucency, humeral migration/ subsidence (relative to 3 month time point), glenoid radiolucency, glenoid migration/subsidence (relative to 3 month time point), device disassembly or fracture, and/or periprosthetic fracture, as described in the radiographic protocol.
 - No reoperation, removal, or modification of any study component up to the subject's completion of the study.
 - No serious device-related complications up to the subject's completion of the study.

For a patient to be considered a success, he or she must meet all the above criteria.

- Secondary Endpoints: The secondary endpoints include:
- Adjusted Constant score and radiographic success evaluated at each time point
 - The percentage of patients achieving an Adjusted Constant Score ≥ 70 at each time point.
 - SF-36
 - VAS
- Inclusion Criteria
1. The subject is ≥ 21 years of age
 2. The subject has continued symptoms in target shoulder despite at least 3 months of other treatments (e.g.: anti-inflammatory, physical therapy and steroid injections)
 3. The subject has a diagnosis in the target shoulder of one or more of the following: osteoarthritis, avascular necrosis, post-traumatic arthritis, or rheumatoid arthritis. The above are defined as follows:

Osteoarthritis (Kellgren-Lawrence Grade 3 or higher), with clinical history of an absence of major trauma to the joint; symptoms of pain, stiffness, swelling and/or loss of motion; and with radiographic evidence of joint space narrowing, sub-chondral sclerosis, peripheral osteophytes with or without posterior subluxation of the humeral head.

Avascular Necrosis (Staging System of Cruess Stage IV or higher), with a clinical history of a known risk factor for avascular necrosis; symptoms of pain and loss of motion; and radiographic findings of flattening or collapse of the humeral head and joint space narrowing.

Post-Traumatic Arthritis (Kellgren-Lawrence Grade 3 or higher), with a clinical history of trauma to the targeted shoulder and subsequent pain, stiffness, swelling and loss of motion; and with radiographic evidence of joint space narrowing, sub-chondral sclerosis, peripheral osteophytes.

Rheumatoid Arthritis (American College of Rheumatology classification score of 6 or higher), with a clinical history that demonstrates: morning stiffness for at least 1 hour and present for at least 6 weeks, swelling, loss of motion, and/or serum rheumatoid factor; and radiographic findings of narrow joint space, peri-articular osteopenia, and/or peri-articular erosions and medial glenoid erosion.
 4. The subject presents with pain and functional impairment in the index shoulder, measured by an Adjusted Constant Score of ≤ 50 .
Note: The Adjusted Constant Score will be calculated from the raw

Constant Score to establish patient eligibility.

5. The subject is willing to receive implantation of the ArthroX's Eclipse or Univers II total shoulder joint replacement.
6. The subject must be physically and mentally willing and able to comply with all study procedures (including follow-up visits and radiographic assessments) until the conclusion of the study.
7. The subject has been informed of the nature of the study and has provided written consent as approved by the local Institutional Review Board or Ethic Review Board.

Exclusion Criteria

1. The subject is a likely candidate for hemi-humeral arthroplasty (i.e.: Avascular Necrosis of the humeral head without glenoid involvement (Stages 0-3); Rotator Cuff Deficient Shoulder, Glenoid Bone deficiency/deformity that precludes glenoid replacement (Walch Type B2 or C) or fractures of the Proximal Humerus, without Glenoid involvement.
2. The subject has immature bone as defined by the absence of cancellous bone patterning, a mature, thick cortex, and stress lines within the cancellous bone.
3. The subject has obvious defects in bone quality, such as cysts or lesions, in the humeral head of the target shoulder, as demonstrated by radiographic evaluation
4. The subject has on the target shoulder a rotator cuff that is not intact and not reconstructible.
5. The subject has irreducible 3- and 4- part proximal humeral fractures of the target shoulder.
6. The subject has documented history of foreign-body sensitivity.
7. The subject is pregnant, or lactating, or intends to become pregnant during treatment period
8. The subject has documented diagnosis of Schizophrenia, Bipolar Disorder and/or Major Depressive Disorder as defined by DSM IV.
9. The subject is skeletally immature as demonstrated radiographically by incomplete closure of proximal humeral epiphyses.
10. The subject is at high risk for poor healing or confounding outcomes (i.e.; clinically significant renal, hepatic, cardiac, hematologic diseases or endocrine disease).
11. The subject is on immune-stimulating or immunosuppressive agents.
12. The subject has co-morbidities that reduces life-expectancy to less than 36 months.
13. The subject is seeking workman's compensation for shoulder injury.
14. The subject is \geq 350 lbs.
15. The subject engaged in heavy labor (e.g. repetitive lifting in the excess of more than 50 lbs.)
16. The subject has had surgery in the affected shoulder in the last 12 months (with the exception of a diagnostic arthroscopy without any reconstruction or repair procedures)

17. The subject is engaged in active sports participation. (e.g. weight lifting involving upper extremities or involved in contact sports)
18. The subject is taking medication known to potentially interfere with bone/soft tissue healing (e.g. steroids-with the exception of topical and /or inhalers)
19. The subject is a prisoner or ward of the state.
20. The subject has a documented diagnosis of alcohol and/or substance abuse as defined by DSM IV
21. The subject has an active or chronic infection, either systemic or local.
22. The subject has pathologic fractures of the affected shoulder.
23. The subject has acute trauma of the affected shoulder
24. The subject has osteoporosis defined as a bone density T score of ≤ -2.5 . (A screening Questionnaire for osteoporosis, SCORE (Simple Calculated Osteoporosis Risk Estimation) and MORES (Male Osteoporosis Risk Estimation Score), will be used to screen patients who require a DEXA bone mineral density measurement.

Timeline:	Initial Enrollment:	10/2012
	Last Enrollment:	12/2017
	Last Subject Visit	7/2019
	Last Close-out Visit	10/2019
Study Duration:	
The length of the Study will be 24 months post-operative*.
 
V 1 Screening : -21 days to day 0
 
V2 Surgery: day 0
 
V3 Post-op: 3 months =90 days +/- 14 days
 
V4 Post-op: 6 months = 180 days +/- 30 days
 
V5 Post-op: 12 months =360 days +/- 60 days
 
V6 Post-op: 24 months = 720 days +/- 60days
 
* If the study is prematurely terminated the investigator will promptly inform active subjects to ensure adequate follow-up for the subjects according to their standard of care practices.
	
Monitoring:	
ArthroX Clinical Research [name] [name] Ph.: [contact]
	

2 Introduction

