3.2 Objectives and Study Endpoints

3.2.1 Primary Safety and Effectiveness Objective

The primary safety and effectiveness objective for this study is to demonstrate that the proportion of patients expected to achieve a Month 24 Composite Clinical Success (CCS) criterion among patients implanted with the investigational device (ArthroX's Eclipse) is clinically non-inferior to a control device (ArthroX's UniversTM II). The composite clinical success criterion contains the following components:

- Functional improvement as reflected in the Adjusted Constant score change from baseline to the Month 24 clinical visit,
- Radiographic outcome success at Month 24,
- Absence of reoperations and revisions up to the subject's completion of the study, and
- Lack of serious device related complications up to the subject's completion of the study.

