3.2.2 Primary Endpoint

The primary safety and effectiveness endpoint is 2 Year Composite Clinical Success requiring the following:

- An improvement in the Adjusted Constant Score (for pain, function and range of motion) from baseline (pre-op) to the Month 24 time-point that is ≥ 10 points and a final Adjusted Constant Score ≥ 54 .

- Radiographic success at the Month 24 time-point which is defined as absence of clinically significant humeral radiolucency, humeral migration/subsidence (relative to 3 month time point), glenoid radiolucency, glenoid migration/subsidence (relative to 3 month time point), device disassembly or fracture, and/or periprosthetic fracture, as described in the radiographic protocol
- No reoperation, removal, or modification of any study component up to the subject's completion of the study.
- No serious device-related complications up to the subject's completion of the study.

For a patient to be considered a success, he or she must meet all of the above criteria.

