Should subject discontinuation occur the reason(s) for discontinuation must be documented in the source documents along with notification to ArthroX Clinical Research. Once the End of Study form is completed in the EDC, the subject status will update to “Early Termination”

Subjects who are determined to be “Early Termination” from the study will not be replaced.

Complete:

Subjects that are screened, randomized, implanted with the Univers II or the Eclipse and completed the 24 month (720 days +/- 60days) follow up Visit 6 will be considered Complete.

- Once the data for visit 6 is entered in the EDC and the End of Study form, the subject status will update to complete.

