5. Lack of serious device related complications (defined as a severe device-related adverse event) up to the subject's completion of the study.

Per the World Health Organization Definition of adverse events, a Grade 3 (or severe) adverse event significantly limits the patient's ability to perform routine activities despite symptomatic therapy.

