10.7 Safety Analysis

All safety endpoints will be summarized separately for investigational and control groups. Similarly, listings with details of the specific complications will be summarized separately as well.

The CCS Component Safety endpoint is any serious, definitely device-related adverse event within 24 Months of surgery. This will be evaluated at the exact two year anniversary (i.e., relative day 730) after the implantation surgery. The safety hypothesis of investigational verses control equality in the likelihood of serious device-related adverse event will be tested using a two-sided Fisher's Exact Test with Type I error rate set to $\alpha=0.05$.

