10.8 Treatment of Missing Data

As previously described, patient success will be defined at Month 24 postoperatively on the basis of a Composite Clinical Success (CCS) criterion. If the Month 24 CCS endpoint is missing due to a clinical evaluation (i.e., Constant score or radiographic results) unavailable at the Month 24 interval but available at a later date (i.e., after the end of the Month 24 interval), the later clinical evaluations will be used to impute missing values. The roll-back imputation is typically considered conservative since in most orthopedic study, maximum recovery is achieved earlier than 24 Months.

It is expected that there will be at least a few patients with missing Month 24 CCS despite the use of Month 24+ roll-back for clinical and radiographic components of the Month 24 CCS. A tipping point analysis will be performed in order to assess the impact of missing data on primary non-inferiority comparisons. Sequentially, at each stage of the tipping point analysis, one missing Month 24 CCS in the investigational device group will be considered as a failure while at the same time one missing value in the control group will be considered a success. Tipping point stages will be sequentially assessed until there are no more missing CCS values in either group.

If the percentage of missing CCS is more than small, e.g., >10%, then the primary sensitivity analysis will involve multiple imputation (Rubin DB, 1991) (MI) rather than tipping point analysis.

MI minimizes the effects of selection bias on the estimates of the proportions achieving Month 24 CCS. A logistic regression method for monotone missing data using SAS procedure Proc.MI (SAS Institute INC, 2006) will be employed to produce multiply imputed outcome determinations for patients missing Month 24 CCS. This method first fits a

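### The two event components of the primary composite carry contradictory cut-off dates, and the roll-back rule does not exclude evaluations made after a revision

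*Combined protocol and SAP*

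**What the plan says.** **Anniversary rule.** The Primary Objective in the Protocol Summary lists "Absence of reoperations and revisions to the exact two-year anniversary of the index surgery, and"; its next bullet sets the same limit for serious device-related complications. For the CCS safety component, Section 10.7 states: "This will be evaluated at the exact two year anniversary (i.e., relative day 730) after the implantation surgery".

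**Completion rule.** The Primary Endpoint in the same Summary and Section 3.2.2 both require "No reoperation, removal, or modification of any study component up to the subject's completion of the study", and item 4 of the CCS list in Section 10 repeats it. Section 3.2.1 has "Absence of reoperations and revisions up to the subject's completion of the study, and". For complications, CCS item 5 reads "Lack of serious device related complications (defined as a severe device-related adverse event) up to the subject's completion of the study", and the Summary endpoint and Sections 3.2.1 and 3.2.2 agree with it.

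**Visit timing.** The Summary gives "V6 Post-op: 24 months = 720 days +/- 60days". Section 6.1.3 ties completion to that visit: a subject who was implanted and "completed the 24 month (720 days +/- 60days) follow up Visit 6 will be considered Complete".

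**Late evaluations.** Under Section 10.8, if the Month 24 Constant score or radiographic result is missing but one exists from after the Month 24 interval, "the later clinical evaluations will be used to impute missing values". The section sets no latest date and does not mention reoperation.

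**The concern.** Reoperation and serious device-related complication are each enough to make a patient a primary failure, so the date at which counting stops decides individual outcomes. With two dates in force and nothing to say which governs, the analyst would have to choose after the data exist.

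Neither date lines up with the evaluations. Counting to the anniversary can stop before the score and film are taken. Counting to completion can stop before two years have passed.

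The roll-back rule adds a separate route. Section 10.8 defends roll-back as conservative because recovery usually peaks before 24 months. That reasoning assumes the same implant throughout and gives no support for a score obtained after the implant was revised. At stake is whether a failed implant could be scored as a success on the result of its revision.

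**Working it through.** **1. The plan's own figure.** Section 10.4 assumes 88% success in both arms, a margin of 0.10, one-sided alpha 0.05, 80% power and 2:1 allocation. Control n = (1.6449 + 0.8416)² × 0.88 × 0.12 × (1 + 1/2) / 0.10² = 97.9, rounded up to 98. Eclipse is then 196 and the total 294, as stated. Dividing each arm by 0.85 gives 116 + 231 = 347, also as stated. The event cut-off does not enter this calculation.

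**2. The dates.** Visit 6: 720 − 60 = day 660 to 720 + 60 = day 780. The anniversary is day 730.
- Anniversary rule: up to 780 − 730 = 50 in-window days (731 to 780) go uncounted.
- Completion rule: a patient seen on day 660 has 730 − 660 = 70 days to the anniversary uncounted. A patient seen exactly on target, day 720, has 10.

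The radiographic protocol gives ±1 month for the Month 24 film (days 690 to 750 with 30-day months). This narrows the film dates, but they still fall on both sides of day 730.

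**3. The same patient under each rule (reoperation component).**

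| Case | Anniversary rule | Completion rule |
|---|---|---|
| Reoperated day 740, Visit 6 on day 770 | Not counted; score and film come after the revision | Failure |
| Visit 6 on day 660, reoperated between then and day 730 | Failure, if the event becomes known (no scheduled visit follows) | Not counted |
| Visit 6 missed, revised in month 27, examined in month 30 and rolled back | Not counted; score and film come after the revision | Unclear |

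The last cell is unclear because Section 6.1.3 defines completion only through a Visit 6 on days 660 to 780. A patient who never had that visit has no defined completion date. If it is the date of termination, the revision is not counted; if it is the month 30 examination, it is.

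**4. Size of the in-window gaps.** The documents give no reoperation rate for these devices, so I assume a two-year rate r of 1%, 3%, 5% or 10% at constant hazard. The probability of a first reoperation in a gap of g days is 1 − (1 − r)^(g/730). For example, r = 10% and g = 50 gives 0.00719, and 196 × 0.00719 = 1.4. To obtain the largest gap, every visit is placed at the extreme day.

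| Assumed r | Days 731–780: Eclipse (196) | Control (98) | Days 661–730: Eclipse (196) | Control (98) |
|---|---|---|---|---|
| 1% | 0.1 | 0.07 | 0.2 | 0.09 |
| 3% | 0.4 | 0.2 | 0.6 | 0.3 |
| 5% | 0.7 | 0.3 | 1.0 | 0.5 |
| 10% | 1.4 | 0.7 | 2.0 | 1.0 |

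These are upper values: visits are aimed at day 720, and a patient changes status only if every other component is passed.

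**5. Effect per patient.** 1/196 = 0.5 point for Eclipse. For control, 1/98 = 1.0 point, or 1/77 = 1.3 points if control randomization stops at 77 as Section 3.1 allows. If the hazard is equal in both arms, the same fraction of each arm is affected (at r = 10% over 50 days, 1.409/196 = 0.705/98 = 0.7%), so the expected difference barely moves. Chance imbalance or unequal hazards would move it.

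**6. Roll-back.** It applies only when the Month 24 evaluation is missing. The documents give no basis for how many such patients return later, so I put no number on this route.

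**The case against.** The strongest reply is that the anniversary wording for reoperation occurs in one objective bullet. The Summary's own endpoint, Sections 3.2.1 and 3.2.2 and CCS item 4 all use completion, and every criterion must be met. On that reading the day 740 patient fails. This stands as a limit on the point. A reader might infer that a patient revised after day 730 simply passes; the documents do not support that, because it follows only from the minority wording or from the undefined roll-back case. But the anniversary is not a lone slip: Section 10.7, in the statistical section itself, applies it to the complication component, and no passage says which rule governs.

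On roll-back, one can argue that a patient examined in month 30 for the study had not completed it in month 27, so the revision counts. That is sensible but unwritten, and Section 6.1.3 points elsewhere. One can also argue that a film after conversion would be hard to grade, because migration is compared with Month 3 and the nine Eclipse zones are specific to that implant. That would block some cases, but the plan does not exclude them.

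Two further inferences fail:
- An evaluation on day 660 cannot show the result of a revision after day 730, because it precedes it. An early visit creates the opposite gap.
- The Visit 6 window has 121 days, of which 70 (58%) precede the anniversary. Even if visits were evenly spread, that is the share seen early, not the share misclassified; nearly all of those patients would have no reoperation in the gap.

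Nor do the documents show that patients who miss Visit 6 come back because of trouble with the shoulder.

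**Conclusion.** The contradiction is real and lies in the definition of the primary endpoint, for reoperations and for serious device-related complications alike. The completion wording, though it predominates, does not clearly cover a rolled-back evaluation, so a score and film made after a revision could fill the Month 24 components.

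The numerical effect is small: at most about 2 Eclipse patients in either in-window gap, or about 1 point against the 10-point margin. This rests on the assumed 1% to 10% two-year rates, constant hazard and all visits at the extreme day; roll-back cases would be additional. The 294 evaluable and 347 randomized are unaffected. It should be corrected because it leaves a rule that decides individual primary outcomes open to choice after the data are seen, not because it is likely to reverse the conclusion.

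**What to change.** 1. Reconcile the Summary objective, Summary endpoint, Sections 3.2.1 and 3.2.2, CCS items 4 and 5 and Section 10.7 to one cut-off, the same for reoperations and for serious device-related complications.
2. Word that cut-off so that any reoperation, removal or modification occurring before the Constant score or the film used for a patient's CCS makes that patient a failure.
3. Add one sentence to Section 10.8: an evaluation made after a reoperation may not be rolled back as a Month 24 value.

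The cost is protocol and SAP wording. No added visit, telephone contact or change in sample size is needed.
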